### **7.3 Method of Treatment Assignment**

All subjects who meet all eligibility criteria, including Exclusion Criterion #13, will be enrolled into Cohort 1. All Cohort 1 subjects will receive the following vaccines:

- Tdap
- PPSV23
- Seasonal Influenza Vaccine

Cohort 2 may be opened for enrollment at any time determined by the Sponsor. Subjects who meet all eligibility criteria, with the exception of Exclusion Criterion #13 will be enrolled in Cohort 2. Subjects who meet all eligibility criteria, including Exclusion Criterion #13, will continue to be enrolled in Cohort 1 throughout the time both cohorts are open for enrollment. All Cohort 2 subjects will receive the following vaccines:

- Tdap
- PPSV23

### **7.4 Packaging and Labeling**

Not applicable

### **7.5 Investigational Product Accountability and Disposal**

All vaccine supply will be accounted for in accordance with GCP. If errors or damages in the vaccine supply shipments occur, the Investigator should contact the Clinical Monitor immediately. Each Investigator will provide copies of the vaccine accountability records for inclusion in the Trial Master File after database lock. The Clinical Monitor will periodically check the supplies of vaccine held by the Investigator or pharmacist to verify accountability of all supply used.

The Investigator will provide the vaccines only to the identified subjects of this study, according to the procedures described in this study protocol. After the end of the study, the Clinical Monitor will perform final accountability.

Celgene (or designee) will review with the Investigator and relevant site personnel the process for investigational product return, disposal, and/or destruction including responsibilities for the site versus Celgene (or designee).

## **7.6      Investigational Product Compliance**

It is the Investigator's responsibility to ensure subjects are fully compliant with their DMT. Drug compliance will be based on subject report and recorded in source documents.

## **8           CONCOMITANT MEDICATIONS AND PROCEDURES**

All concomitant treatments, including blood and blood products, used from 30 days prior to Day 1 until Day 28, must be reported on the CRF along with dosage information, dates of administration, and reasons for use. For medications with a single active ingredient, generic names for concomitant medication should be used, if possible. For combination products, brand names should be used. The total daily dose should be filled in whenever possible.

Treatment for symptoms related to MS (eg, spasticity, incontinence, pain, fatigue, and depression) is not restricted, but Investigators should attempt to keep therapies or treatments reasonably constant throughout the study period. Changes may be made if appropriate for a subject's well-being in the clinical judgment of the Investigator.

### **8.1      Prohibited Concomitant Medications and Procedures**

**The following medications cannot be used during the trial through the End of Treatment Visit:**

- Any medications prohibited by the product labels of country for ozanimod and IFN- $\beta$  compounds
- Any approved and unapproved disease-modifying MS agents, excluding ozanimod and IFN- $\beta$
- Treatment with Class Ia or Class III anti-arrhythmics (examples of prohibited systemic cardiac medications are provided in [Table 6](#) ) or treatment with a combination of 2 or more agents known to prolong PR interval (eg, combination of a beta blocker and verapamil) are prohibited during the study unless approved by the Sponsor's representative. Note that [Table 6](#) does not provide a comprehensive list. The Medical Monitor should be contacted for further guidance if needed.
- Systemic corticosteroid therapy or ACTH, except for treatment of protocol-defined treatment of relapses. Corticosteroids that are by non-systemic routes (eg, topical, inhaled, intra-articular) are allowed.
- Any vaccine, including first or second dose of COVID-19 vaccine
- Intravenous immunoglobulin (IVIg) or plasmapheresis
- Immunosuppressive agents known to deplete lymphocytes
- Breast cancer resistance protein inhibitors (eg, cyclosporine, eltrombopag)
- Monoamine oxidase inhibitors (eg, selegiline, phenelzine)
- CYP2C8 inhibitors (eg, gemfibrozil and clopidogrel) or inducers (eg, rifampicin)

**Table 6: Examples of Prohibited Cardiac Medications (Systemic Use)**

Pharmaceutical Class	Example Medications
Class Ia or Class III Antiarrhythmic drugs	amiodarone, bepridil hydrochloride, disopyramide, dofetilide, dronedarone, flecainide, sotalol, ibutilide, lidocaine, procainamide, propafenone, quinidine, tocainide

**8.2 Required Concomitant Medications and Procedures**

Not applicable

## **9 STATISTICAL CONSIDERATIONS**

Detailed methodology for summary and statistical analyses of the data collected in this study will be documented in a Statistical Analysis Plan, which will be maintained by the Sponsor.

### **9.1 Overview**

This is a non-randomized, open-label study in which all subjects remain on their pre-study (baseline) treatment per protocol. Subjects will be recruited by investigators from MS clinical practice patients and prospectively assessed for immune response to vaccination. The statistical analyses will focus on estimating immune response rates, adjusting for baseline subject-level characteristics. No formal statistical hypothesis is evaluated. To mitigate for potential differences in the recruited subject population in the ozanimod and non-ozanimod arms that potentially could affect immune response, response rates will be estimated based on a logistic regression model adjusting for several factors, eg, age, sex, body mass index (BMI), and baseline absolute lymphocyte count (ALC). The results of the statistical analyses for immune response endpoints will be summarized for subjects receiving ozanimod (ozanimod arm) and subjects not receiving ozanimod (non-ozanimod arm) as their standard of care disease modifying therapy for MS. Analyses of safety will be summarized by descriptive statistics separately for the ozanimod and non-ozanimod arms.

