#### **1.3.4 Rationale for Selected Study Design**

This study will use a prospective, open-label design with subjects receiving vaccines at a single visit followed by immune response and safety assessments 28 days later in subjects on steady state ozanimod compared to subjects receiving IFN- $\beta$  as a reference control or not receiving DMT treatment. Using a control group of subjects treated with IFN- $\beta$  is supported by vaccination studies in MS subjects on IFN- $\beta$ s which show similar post-vaccination immune responses to MS subjects receiving no DMT (Olberg, 2014; Olberg, 2018; Mehling, 2013) and subjects on IFN- $\beta$ s have been successfully used as controls in other MS DMT vaccine response studies (Bar-Or, 2013; Olberg, 2020; Von Hehn, 2018). Multiple vaccines administered during a single visit are well established in children and recommended for adults as safe, tolerable, and are not likely to reduce immune response (King, 1994; Broderick, 2016; Ferlito, 2021). Open-label designs are acceptable to assess the effects of immune modulating therapies on vaccine response and by vaccine manufacturers to assess vaccine immunogenicity (Schwid, 2005; Bar-Or, 2013; Olberg, 2018; Von Hehn, 2018). Laboratory studies, including the immunological correlates that assess the humoral response to vaccines (eg, serum antibody concentrations or antibody titers) provide objective assessments of vaccine response as substitute endpoints for longer term studies that measure clinical protective effect (Madore, 2010). The specific laboratory criteria used to establish vaccine immunogenicity is vaccine dependent. In general, vaccine responses are assessed by comparing post-vaccination to pre-vaccination antibody levels and by determining whether responses surpass a minimum threshold for seroprotection or an increase in antibody titers/concentrations to produce a serologic response (WHO, 2013). The laboratory criteria used in this study are based on guideline recommendations and correlates of humoral immunity (EMA, 1997; Qin, 2007; FDA, 2007; Plotkin, 2008). To mitigate the differences in the recruited subject population, this study will define eligibility criteria to reduce potential confounding variables affecting immune response to vaccination. Despite well-defined eligibility criteria, to account for potential confounders that could affect immune responses, serological response criteria will be compared based on a model adjusting for appropriate factors (eg, age, sex, body mass index [BMI], and baseline absolute lymphocyte count [ALC]).

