### **4.2 Inclusion Criteria for All Subjects**

Subjects must satisfy the following criteria to be enrolled in the study:

1. Male or female subjects 18 to 65 years of age, inclusive, at the time of signing the ICF.
2. Subject must understand and voluntarily sign an ICF prior to any study-related assessments/procedures being conducted.
3. Subject is willing and able to adhere to the study visit schedule and other protocol requirements.
4. Subject has a diagnosis of MS according to the 2017 revision of the McDonald diagnostic criteria and has RMS: RRMS or secondary progressive MS with active disease based on recent clinical relapse or MRI lesion activity ([Thompson, 2018](#))
5. At Screening, subjects must be on one of the following three treatment options and willing to remain on the same treatment for the duration of the study:
  - a. Treatment with ozanimod (0.92 mg maintenance dose). Ozanimod treatment must have been initiated at least █ days prior to the Day 1 Visit. Subjects should be compliant with the ozanimod label. In addition, in the █ days prior to Day 1, ozanimod treatment must not have been interrupted for more than 1 day.
  - b. Treatment with a non-pegylated form of IFN- $\beta$  and compliant with dosing within █ of Day 1 per the manufacturer's label
  - c. No treatment with a DMT for RMS
6. Subject is ambulatory (with or without walking aid) at Screening.
7. Subject is relapse-free in the 30 days prior to Day 1; during this period, subjects must have been clinically stable, without systemic corticosteroid or adrenocorticotropic hormone treatment.
8. Subjects who receive ozanimod or non-pegylated IFN- $\beta$  as their standard of care medication must do so in accordance with the local drug label.
9. Females of childbearing potential (FCBP) who receive ozanimod as their standard of care medication must agree to use contraception according to the approved local label.

All Subjects:

Periodic abstinence (calendar, symptothermal, post-ovulation methods), withdrawal (coitus interruptus), spermicides only, and lactational amenorrhoea method (LAM) are not acceptable methods of contraception. Female condom and male condom should not be used together.

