- c. Vital signs include sitting blood pressure, body temperature and resting pulse. A subject should have rested in sitting position, preferably for at least 5 minutes before measuring blood pressure and pulse. The same arm should be used for blood pressure measurement throughout the study. Body temperature is measured by oral, tympanic, or with temporal thermometer. Manual and digital thermometers are allowed. Resting pulse should be determined by manual palpation according to standard clinical practice. The method for measuring blood pressure, pulse, and temperature should be documented and the same method should be used consistently throughout all visits.
- d. Height is measured at the Screening Visit with the subject not wearing shoes. Weight is measured at all Visits with the subject wearing no shoes and light clothing. BMI should be calculated prior to enrollment.
- e. Both physical examination and symptom-oriented physical examination will include neurological examination.
- f. Day 1 (baseline) and End of Study (Day 28) clinical laboratory tests include serologic antibody testing for COVID-19 (baseline only), chemistry (full panel), hematology, and urinalysis
- g. If needed, ALC may be measured for subjects with prior S1P modulator-related lymphopenia if no laboratory data are recorded meeting protocol criteria. Clinical laboratory testing, while not required for screening eligibility except as described in the protocol, may be performed for valid medical concerns after discussion with the medical monitor.
- h. Blood draw for titer determinations at relapse visit should occur prior to administration of any steroids.
- i. For subjects on ozanimod only. Record the time of PK sample collection and the time of the most recent ozanimod dose administration prior to PK sample collection. If █ hours or more pass between (first) PK sample collection and visit completion, draw a second PK sample immediately prior to visit completion and record time. If an ozanimod dose is administered after the first PK sample collection, record time of administration and collect second PK sample immediately prior to visit completion and record time. For all subjects, plasma sample for biomarker evaluation will be included (eg, inflammatory markers) and COVID-19 antibodies.
- j. Cohort 1 will receive Tdap, PPSV23, and influenza vaccine; Cohort 2 will receive Tdap and PPSV23.

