## 6.2 Treatment Period - Day 1/Baseline

The following evaluations will be performed at the frequency specified in [Table 3](#). The evaluations should be performed prior to vaccine administration on Day 1, unless otherwise specified.

- Review of subject eligibility
- Confirmation and source documentation by the PI that subjects have taken ozanimod or IFN- $\beta$  as prescribed by the manufacturer label and as required in the inclusion criteria
- Concomitant medications evaluation
- AE evaluation
- Urine pregnancy test confirmed negative for pregnancy
- Vital signs (including blood pressure, temperature, and heart rate)
- Symptom oriented physical examination
- Urinalysis and blood sampling for the follow laboratory tests:
  - Serologic antibody testing for COVID-19 and other PD parameters
  - Hematology: red blood cell (RBC) count, total and differential white blood cell (WBC) count (basophils, eosinophils, lymphocytes, monocytes, and neutrophils), platelet count, hemoglobin, hematocrit, mean corpuscular volume (MCV), mean corpuscular hemoglobin (MCH), and mean corpuscular hemoglobin concentration (MCHC).
  - Blood Chemistry: sodium, potassium, chloride, calcium, magnesium, phosphate, blood urea nitrogen, glucose, albumin, alkaline phosphatase, creatinine, alanine aminotransferase (ALT) (SGPT), aspartate aminotransferase (AST) (SGOT), gamma-glutamyl transferase (GGT), total bilirubin, and conjugated bilirubin. Abnormal laboratory parameters inconsistent with clinical presentation of MS or suspicious of underlying medical condition should be repeated for accuracy.
- Efficacy assessments, including blood draw for pre-vaccination antibody titer determination, and blood draw for PK (see [Section 6.4](#))
- Administration of Tdap, PPSV23, and influenza vaccine (Cohort 1 only), (intramuscularly or subcutaneously, as described in [Table 4](#) )

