#### **9.6 Immune Response Analysis**

The primary endpoint analysis and all analyses for immune-response to vaccination will be performed in the per-protocol population, ie, in subjects who received the correctly assigned vaccinations and had no major protocol violations. Sensitivity analyses will be conducted within the mITT population consisting of all subjects who received at least one vaccination and summarized according to their initial treatment status (ozanimod vs non-ozanimod) regardless of protocol violations

If Cohort 2 is initiated, then not all subjects will receive the seasonal inactivated influenza vaccine. For the purposes of summarizing the Tdap and PPSV23 vaccines, all subjects in Cohorts 1 and 2 will be combined, since they generally would have had the opportunity to receive all three vaccines. For evaluating the seasonal inactivated influenza vaccine, the analyses will be based on Cohort 1 subjects.

The ozanimod and non-ozanimod treatment group immune response rates and differences will be estimated based on a model adjusting for baseline demographics (eg, age, gender, BMI, baseline ALC, etc). We note the estimates of treatment differences should be interpreted with caution, since, in addition to the limited sample size, the ozanimod and non-ozanimod arms are not randomized. Some or all of the aforementioned factors may not be feasible to include in the analysis model. Analysis details will be provided in the statistical analysis plan such as the required number of subjects within each factor stratum (eg, if within a factor stratum level there are less than 10 subjects, then that factor will be excluded from the model).

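### Day 1 ALC, an example covariate for the arm comparison, is measured on steady-state ozanimod, so adjusting for it would remove any part of the drug's effect that runs through ALC

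*Combined protocol and SAP*

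**What the plan says.** Section 9.1 estimates response rates from a logistic regression "adjusting for several factors, eg, age, sex, body mass index (BMI), and baseline absolute lymphocyte count (ALC"). Section 9.6 applies "a model adjusting for baseline demographics (eg, age, gender, BMI, baseline ALC, etc") to the rates and to the difference between arms. The Protocol Summary (Statistical Methods) repeats the list, and Section 1.3.4 says that "serological response criteria will be compared based on a model adjusting for appropriate factors", again with ALC as an example. The stated aim is to offset differences between the recruited populations.

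On timing, Section 1.3.4 describes assessment "28 days later in subjects on steady state ozanimod". Inclusion criterion 5a sets a minimum time on drug before Day 1 ("Ozanimod treatment must have been initiated at least" a number of days that is redacted). Table 3, footnote f, begins "Day 1 (baseline) and End of Study (Day 28) clinical laboratory tests include" and goes on to list hematology. Section 6.2 specifies the Day 1 panel as including "total and differential white blood cell (WBC) count (basophils, eosinophils, lymphocytes, monocytes, and neutrophils"). No ALC from before ozanimod is scheduled.

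The list is provisional. Section 9.6 says some or all factors may prove infeasible, leaves details to the SAP, and gives an example rule: "if within a factor stratum level there are less than 10 subjects, then that factor will be excluded from the model".

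**The concern.** A covariate used to offset differences between recruited groups should not itself be changed by the exposure under study. Three statements in the protocol suggest that Day 1 ALC is:

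- Section 1.2: ozanimod sequesters lymphocytes in lymphoid tissue.
- Section 1.3.1: by its mechanism it could reduce vaccine response. Measuring this is the purpose of the study, and the data are meant to support the label.
- Section 1.3.4: profound lymphopenia could affect vaccine response.

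Together they place on-drug ALC on a plausible path from ozanimod to the outcome. A model that compares the arms at equal ALC leaves out whatever travels along that path. The text does not say whether the total difference or an ALC-conditional difference is wanted, and it specifies no estimate without ALC. The risk is that an ALC-conditional result is read as ozanimod's effect on vaccine response.

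**Working it through.** **The plan's own figures (Section 9.3).** For n = 30 and p = 0.45, 1.96 × √(0.45 × 0.55 / 30) = 0.178. Averaged over the binomial distribution of the estimate, the half-width is 0.1749, which matches the stated 0.175. The binomial 2.5% and 97.5% points are 8/30 = 0.267 and 19/30 = 0.633, also as stated. These describe one unadjusted proportion and do not depend on the covariate list.

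**Inputs.** From Section 9.3: 45% (ozanimod) and 60% (non-ozanimod), 30 per arm, so a 15-point deficit. From Section 1.3.4: 0.5 × 10⁹/L is about the 25th percentile of ALC in the pivotal trials, with no arm or visit given. Assumed: that percentile applies to on-drug ozanimod ALC; ALC is log-normal with log-SD 0.4 to 0.6; the control median is 1.3 to 1.8; nothing confounds ALC and response.

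**Model.** logit p = a + b·arm + c·log ALC, with ozanimod log-mean = ln 0.5 + 0.674 × SD (median 0.65 to 0.75). The three coefficients are set so that the marginal rates are 0.45 and 0.60 and a chosen share of the −0.15 runs through ALC: E[p(ozanimod, ozanimod ALC)] − E[p(ozanimod, control ALC)] = share × (−0.15). Each arm's rate is then standardised to the pooled ALC distribution.

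**Adjusted deficit in points.** The first four rows are large-sample; ranges run over the assumed distributions.

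| Form of ALC | 0% mediated | 25% | 50% | 100% |
|---|---|---|---|---|
| log-ALC, continuous | 15.0 | 11.3 | 7.6 | 0.0 |
| untransformed, continuous | 15.0 | 12.0–12.5 | 8.9–9.8 | 2.0–4.1 |
| split at 1.0 (assumed cut) | 15.0 | 12.7–12.8 | 10.3–10.6 | 5.2–6.0 |
| split at 0.5, always kept | 15.0 | 13.6–14.4 | 12.2–13.8 | 9.2–12.5 |
| split at 0.5, under-10 rule, 30 per arm (mean) | – | 14.4–14.8 | 13.2–14.7 | 11.9–14.5 |

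The last row is a loss of 15 − 14.8 = 0.2 to 15 − 11.9 = 3.1 points.

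**The rates move too.** With continuous log-ALC, the standardised ozanimod rate is 48.7–48.8% at 50% mediation and 52.5% at 100%, against a true 45%. The control rate falls to 56.3% and 52.5%, against 60%.

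**Why the rule matters.** At a 0.5 cut, 25% of ozanimod subjects fall below by construction, and 0.07% to 5.6% of controls. The probability that both strata hold at least 10 of 60 is 0.199 to 0.437, so ALC usually drops out.

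**Precision with no mediation (SD of the difference, 30 per arm).** Unadjusted 0.13; continuous log-ALC 0.14–0.20; split at 0.5, 0.13–0.14.

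**The opposing bias.** Suppose a prior-treatment group is 5 to 25 percentage points more common in one arm and responds 10 to 30 points less often (both assumed). Leaving out ALC could then leave in 0.05 × 0.10 = 0.5 to 0.25 × 0.30 = 7.5 points of confounding, in either direction.

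**The case against.** The strongest reply is that this criticises an example. ALC appears only as an illustrative factor, Section 9.6 says factors may be dropped, and the detail belongs to a SAP whose analysis text is not in the material reviewed. That stands: a reader might infer that the plan commits to an ALC-adjusted model, and it does not. The example exclusion rule, however, screens for sparse strata. It would drop or keep ALC according to counts, whatever question is being asked.

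Second, the loss may be small. The only ALC cut the protocol ties to vaccine response is 0.5, and with the under-10 rule the loss there is about 0 to 3 points, against an unadjusted 95% half-width of 1.96 × √(0.45 × 0.55/30 + 0.60 × 0.40/30) ≈ 0.25 for the difference. This also stands. The larger losses need ALC to enter in another form or always be kept, and no passage specifies the form or the mediated share.

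Third, the calculation contains no confounder, so adjustment can only shrink the deficit in it. A reader might infer that adjustment must pull the difference towards zero. The documents do not support this: Section 1.3.4 foresees lingering lymphopenia from earlier S1P modulators in either arm, and criterion 17e admits subjects 60 days after fingolimod, so ALC may carry real confounding. Nor do they support calling ALC strongly tied to arm, since no levels by arm are given; the precision costs above rest on assumption.

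Finally, no hypothesis is tested and Section 9.6 already urges caution about differences. That caution cites sample size and lack of randomisation, and does not mention a covariate measured on drug.

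**Conclusion.** The point holds as a cheap improvement to the plan. Day 1 ALC in the ozanimod arm is at least partly a consequence of the drug, and following the named covariate list would remove any ALC-mediated part of the effect from the reported rates and difference. How much is unknown. Under the stated assumptions, including no confounding, it ranges from nothing to the whole 15 points with continuous log-ALC, and is about 0 to 3 points with a 0.5 split and the under-10 rule. The possible confounding of 0.5 to 7.5 points overlaps these ranges, so which bias is larger is not established.

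It would be tempting to read the ALC-adjusted result as ozanimod's direct effect, free of ALC. That requires no unmeasured causes shared by ALC and response, and earlier treatment is a candidate for one. The consequence is for interpretation of the estimates; no pass or fail decision depends on it.

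**What to change.** In Sections 9.1 and 9.6, with matching wording in the Protocol Summary, Section 1.3.4 and the SAP:

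- Report the adjusted rates and difference from a model with age, sex and BMI but without Day 1 ALC, as the estimate of the total ozanimod versus non-ozanimod difference.
- Beside it, report the model that adds Day 1 ALC in a form fixed in advance (continuous on a stated scale, or named cut-points). Label it as conditional on an on-treatment variable, and do not present it as a clean direct effect.

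The cost is wording and one extra model, with no new data or subjects. The downside is that the ALC-free model leaves in whatever confounding ALC carries, which is why both should be shown.
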